### 5.2.3 Rationale for the Primary Endpoints

The occurrence of DLTs is considered to be an appropriate endpoint to assess safety and tolerability in this dose escalation Phase I study.

Pharmacokinetic data from approximately 30 Chinese subjects is deemed necessary to meet regulatory requirements and will be used for ethnic sensitivity assessment. The PK of avelumab, a monoclonal antibody binding to a tumor surface target, may present important features, eg, target mediated disposition and nonlinearity. A number of factors, including the dose levels and tumor target expression, may also play a role in the PK and CCI behavior. Pharmacokinetic data will be collected to explore these PK and CCI characteristics.

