**Planned number of subjects:**

Approximately 21 subjects (up to approximately 24 subjects).

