#### 5.1.1.1 Dose Escalation Design

The dose escalation of this study is based on a modified “3 + 3” cohort design. An initial cohort of 3 Chinese subjects with metastatic or locally advanced solid tumors will receive 3 mg/kg of

avelumab (IMP) once every 2 weeks. Each of these first 3 subjects will be observed for 21 days (DLT observation period). The SMC will review the safety data, including DLTs, and advise on further escalation to the next cohort (10 mg/kg of avelumab once every 2 weeks). As this study represents the introduction of avelumab into a new region, the 3 mg/kg dose has been selected as the starting dose, a minus 1 dose level to avelumab 10 mg/kg, as an extra precaution to further mitigate risks in Chinese subjects (Figure 5-3).

The 10 mg/kg once every 2 weeks cohort will enroll 6 Chinese subjects with metastatic or locally advanced solid tumors. Since more than 1400 subjects have been exposed to avelumab at a dose of 10 mg/kg once every 2 weeks and it has been well tolerated, it is unlikely that there are ethnic differences with respect to avelumab safety and PK; therefore staggered enrolment (3 + 3) will not be used for the 10 mg/kg once every 2 weeks cohort and all 6 slots will be opened at the same time for competitive recruitment.

After completion of 10 mg/kg once every 2 weeks cohort, the avelumab dose will be further escalated up to 20 mg/kg once every 2 weeks to characterize the safety and PK of avelumab at a higher dose level. A staggered “3 + 3” enrolment will be used for the 20 mg/kg avelumab cohort.

Once the safety of avelumab at 20 mg/kg once every 2 weeks have been established and can be regarded as safe (ie, no DLT observed in the first 3 subjects or less than 2 out of the 6 subjects experience a DLT), a new cohort of 10 mg/kg administered once weekly can be immediately initiated to assess safety of already established dose strength with a more frequent dose administration. Six (6) evaluable subjects are planned to be included in this cohort. The DLT assessment is not applicable for the 6 subjects in the 10 mg/kg once weekly cohort. Subjects in this cohort will receive avelumab at 10 mg/kg once weekly for the first 12 weeks. Starting from Week 13, dose frequency will be changed to once every 2 weeks. All 6 slots will be opened at the same time for competitive recruitment.

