### 5.1.2.1.2 Dose Escalation Scheme

Subjects will receive avelumab by IV infusion over 1 hour once every 2 weeks. Dose escalation of avelumab will be performed according to the following dose levels, representing a 3.3 or 2 times increase at each escalation. Each subject will receive a fixed dose of avelumab according to their allocated dose level:

- 3 mg/kg
- 10 mg/kg
- 20 mg/kg

The dose escalation criteria are as follows:

For each dose level, DLTs (as defined in Section 7.4.1.1) will be assessed during the 21 days after administration of avelumab. The criteria for moving from 3 mg/kg to 10 mg/kg of avelumab is if no subject experiences a DLT in the first 3 subjects. No additional 3 subjects will be enrolled. If 1 out of the first 3 subjects in the 3 mg/kg cohort experiences a DLT, this cohort will be expanded to 6 subjects. If  $\geq 2$  out of 3 or 6 subjects in the 3 mg/kg cohort experience a DLT, the study will be placed on hold. See also Section 2.1.

[figure not shown]
In the 10 mg/kg once every 2 weeks cohort, 6 slots will be opened at the same time for competitive enrolment of 6 subjects. If less than 2 out of the 6 subjects in this cohort experience a DLT, the dose of 10 mg/kg will be considered safe in Chinese subjects. If 2 or more subjects experience a DLT, the study will be placed on hold.

After completion of the 10 mg/kg once every 2 weeks cohort, the dose of avelumab will be escalated to 20 mg/kg once every 2 weeks in order to characterize the safety and PK of avelumab at a higher dose level. The criteria for moving from 10 mg/kg to 20 mg/kg of avelumab is if less than 2 out of 6 subjects experience a DLT at the 10 mg/kg dose level (once every 2 weeks cohort). Staggered “3 + 3” enrolment will be used for the 20 mg/kg cohort. If no subject experiences a DLT in the first 3 subjects, the avelumab dose level at 20 mg/kg once every 2 weeks will be regarded as safe in Chinese subjects; the additional 3 subjects will be enrolled to fill up the cohort for PK evaluation, but they will not be subjected to further DLT evaluation.

If 1 subject in the first 3 subjects experiences a DLT (confirmed by SMC only), an additional 3 subjects will be enrolled. If less than 2 out of the 6 subjects experience a DLT, the dose of 20 mg/kg will be considered safe in Chinese subjects. If  $\geq 2$  out of 3 or 6 subjects experience a DLT, the 20 mg/kg cohort will be put on hold (the decision will be made by SMC).

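### Protocol 5.2.3 calls PK data from about 30 Chinese subjects necessary, but the planned cohorts supply 21 to 24; a separate minor point is that the SAP leaves the once-weekly cohort out of noncompartmental analysis without declaring it

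*Protocol*

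**What the plan says.** **Number of subjects.** PK is one of the two primary endpoints (Protocol 8.3.1). The rationale in 5.2.3 states: "Pharmacokinetic data from approximately 30 Chinese subjects is deemed necessary to meet regulatory requirements and will be used for ethnic sensitivity assessment". The Synopsis gives the planned number as "Approximately 21 subjects (up to approximately 24 subjects", and its statistical methods paragraph bases the sample size on the 3 + 3 rule, with no statistical assumptions.

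The cohort sizes come from Protocol 5.1.1.1 and 5.1.2.1.2:

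- 3 mg/kg every 2 weeks: 3 subjects, or 6 if one of the first 3 has a DLT.
- 10 mg/kg every 2 weeks: 6 subjects.
- 20 mg/kg every 2 weeks: 6 subjects if the cohort is not held. With one DLT in the first 3, three more are enrolled. With none, "the additional 3 subjects will be enrolled to fill up the cohort for PK evaluation".
- 10 mg/kg once weekly: "Six (6) evaluable subjects are planned to be included in this cohort". This cohort can open only under the condition "Once the safety of avelumab at 20 mg/kg once every 2 weeks have been established and can be regarded as safe".

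**PK parameters.** The Synopsis and Protocol 7.5.1 list the noncompartmental parameters, with AUC0-tau defined for a dosing interval of one or two weeks. Protocol 8.5.2.2 says the 7.5.1 parameters will be reported for the PK Analysis Set and excludes no cohort. SAP 16.1 performs noncompartmental computation for the three every-2-weeks cohorts, calculates the parameters on Day 1 of those cohorts, and sets tau at 336 hours. The SAP abbreviation list still defines AUC0-tau for one or two weeks. SAP Section 7, which lists changes from the protocol, mentions only the biomarker analyses.

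**The concern.** The protocol gives a number of subjects that it calls necessary for a regulatory purpose, then plans a smaller one and does not say how the two fit together. Protocol 3.3 says the study will be part of the marketing submission in China, so the sentence in 5.2.3 will be read by the people it concerns. They cannot tell whether this trial alone is meant to meet the need or whether other Chinese data are to be added.

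The parameter question is smaller and does not bear on the count. A reader of the protocol would expect AUC0-tau, Cmax, half-life and the other parameters for the once-weekly regimen. Under the SAP the report will not contain them, and nothing marks this as a change.

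**Working it through.** **1. The plan's own figure.** Assume that no cohort is held, the once-weekly cohort is opened, no subject is replaced and no dose level is added.

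| Path | 3 mg/kg | 10 mg/kg | 20 mg/kg | 10 mg/kg weekly | Total |
|---|---|---|---|---|---|
| No DLT in first 3 at 3 mg/kg | 3 | 6 | 6 | 6 | 21 |
| One DLT in first 3 at 3 mg/kg | 6 | 6 | 6 | 6 | 24 |

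This matches the planned 21, up to 24. The 20 mg/kg cohort reaches 6 whether its first 3 subjects have no DLT or one, so only the 3 mg/kg cohort moves the total.

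**2. Against 30.**

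- 30 − 21 = 9, and 9/30 = 30%.
- 30 − 24 = 6, and 6/30 = 20%.

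**3. Subjects in cohorts planned for noncompartmental analysis.** Leaving out the 6 once-weekly subjects gives 3 + 6 + 6 = 15, or 6 + 6 + 6 = 18. These are planned maxima, because SAP 16.1 requires sufficient concentration-time data and calculates parameters only where possible.

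**4. What could raise the total.**

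- Protocol 5.1.1.1 allows replacement of subjects who do not meet the dose-determination requirement. A replaced subject can still belong to the PK Analysis Set. Reaching 30 in this way alone needs 6 to 9 replacements.
- The text after Figure 5-3 lets the Safety Monitoring Committee add an interim dose level. No size is given. If it had 3 or 6 subjects (my assumption), the totals would be 21 + 3 = 24, 21 + 6 = 27, 24 + 3 = 27 and 24 + 6 = 30. Only the largest combination reaches 30.

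Neither route is part of the planned number.

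**5. Once-weekly parameters, side by side.**

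| Item | Protocol | SAP |
|---|---|---|
| Subjects covered | PK Analysis Set (8.5.2.2) | Every-2-weeks cohorts (16.1) |
| Tau | 1 or 2 weeks (Synopsis, 7.5.1) | 336 hours (16.1); one or two weeks (abbreviation list) |
| Declared as a change | – | No (Section 7) |

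The scope and the fixed tau settle the matter: 336 hours is 14 days, so a 1-week AUC0-tau is excluded. The sampling schedule is secondary. SAP 16.1 asks for at least 3 valid post-dose concentrations in the profile. In the once-weekly cohort (Protocol 7.5) the Week 1 interval has 2 scheduled post-dose samples: end of infusion and the Week 2 pre-dose. The intervals starting at Weeks 2, 4, 6, 7 and 12 have 1 each, and the other weekly intervals have none. The Day 1 profile of the every-2-weeks cohorts has 12.

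**The case against.** **The 30 may describe the whole submission.** The sentence in 5.2.3 does not say that all 30 come from this trial, and 3.3 places the study within a wider submission. Section 8.1 is redacted and may explain the figure. Both points stand, and they limit the conclusion to the readable text. Against them, the sentence justifies this trial's own primary endpoint. Section 5.2 says the Chinese Health Authority requires a dedicated study that assesses PK, and 5.2.2 calls this the first study in Chinese subjects with solid tumors. The title mentions expansion, but 5.1.1 leaves that to a future study. If another source is intended, naming it resolves the point.

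**The totals are neither a floor nor a ceiling.** This is correct. Replacement or an added level could raise them, and a hold would lower them. A reader might infer a far larger shortfall from the hold rules. I give no figures for that: holds are stopping contingencies and not the planned PK basis. The 10 mg/kg rule reads "If 2 or more subjects experience a DLT, the study will be placed on hold" and does not say whether all six subjects, whose slots open together, would have been enrolled by then.

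**The SAP is entitled to narrow the analysis.** Protocol 8.5.1 leaves full details to the SAP, and SAP 16.1 states the restriction openly. The once-weekly cohort also keeps individual concentration profiles and mean trough profiles. That makes the point minor. It does not remove the conflict with 8.5.2.2 or supply the missing entry in Section 7.

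**The three-sample rule may not block every subject.** The rule counts values in the profile, not per weekly interval. A subject who stops after the first dose might have three: end of infusion, End-of-Treatment visit and 30-day visit. The conclusion therefore rests on the every-2-weeks scope and the 336-hour tau.

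**Conclusion.** The first point holds for the readable text. The trial is planned to supply PK data from 21 subjects, up to 24, where 5.2.3 calls about 30 necessary. The gap is 6 to 9 subjects (20% to 30%), which is more than the word approximately can reasonably cover. This assumes no hold, an opened once-weekly cohort, no replacement and no added dose level. It is a defect in the stated PK basis that should be corrected.

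The second point also holds and is minor. It covers all noncompartmental parameters for the 6 once-weekly subjects, and the 1-week AUC0-tau is one of them.

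Three stronger conclusions might be inferred, and the documents do not support them:

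- That the trial fails a regulatory requirement. The documents do not show whether the 30 applies to this trial alone.
- That the sample size or an analysis is invalid. The size follows the 3 + 3 rule, PK is summarized descriptively, and nothing is calculated or decided from 30.
- That the once-weekly cohort yields no PK results. Its concentrations and trough profiles are still reported.

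**What to change.** **Protocol 5.2.3.** State that this trial is planned to supply PK data from about 21 (up to 24) Chinese subjects, of whom at most 15 to 18 are in cohorts planned for noncompartmental analysis. Then do one of two things:

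- name the source of the remaining Chinese PK data; or
- confirm what is required and correct the figure of 30.

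Deleting the sentence without that confirmation would hide the discrepancy. The new wording should also not suggest that 21 meets a need for 30.

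**SAP Section 7.** Declare that no noncompartmental parameters, including the 1-week AUC0-tau, are calculated for the once-weekly cohort, and that concentrations and trough profiles are reported for it. Align the AUC0-tau definition in the Synopsis, Protocol 7.5.1 and the SAP abbreviation list.

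**Cost.** Wording only, with no extra subjects, samples or analyses. The sponsor has to confirm the origin of the 30, and the stated PK basis of the trial becomes smaller.

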## 5.2.4 Rationale for the Secondary Endpoints

Secondary safety and immunogenicity endpoints will be assessed and used to support evaluation of the primary endpoints.

CCI

## 5.2.6 Inclusion of Special Populations

Not applicable.

## 5.3 Selection of Study Population

Only persons meeting all inclusion criteria and no exclusion criteria may be enrolled in this study. Prior to performing any study assessments that are not part of the subject's routine medical care, the Investigator will ensure that the subject or the subject's legal representative has provided written informed consent.

### 5.3.1 Inclusion Criteria

1. Signed written informed consent.
2. Chinese men or women  $\geq$  18 years of age.
3. Availability of a recently obtained FFPE block containing tumor tissue (biopsy from a non-irradiated area within 6 months) or 12 or more unstained tumor slides suitable for biomarker detection (see Section 7.6).
4. Histologically or cytologically proven locally advanced unresectable or metastatic solid tumor, for which no standard therapy exists or standard therapy has failed.
5. ECOG performance status of 0 or 1 at study entry.
6. Estimated life expectancy of at least 3 months.
7. Adequate hematological function as defined below:

- White blood cell count  $\geq 3 \times 10^9/L$
  - Absolute neutrophil count  $\geq 1.5 \times 10^9/L$
  - Lymphocyte count  $\geq 0.5 \times 10^9/L$
  - Platelet count  $\geq 100 \times 10^9/L$
  - Hemoglobin  $\geq 90$  g/L (may have been transfused).
8. Adequate liver function as defined below:
- Total bilirubin  $\leq 1.5 \times$  upper limit of normal (ULN)
  - Aspartate aminotransferase (AST)  $\leq 2.5 \times$  ULN
  - Alanine aminotransferase (ALT)  $\leq 2.5 \times$  ULN.
9. Adequate renal function as defined below:
- Estimated creatinine clearance  $\geq 50$  mL/min according to Cockcroft-Gault formula.
10. Negative blood pregnancy test at Clinical Screening for women of childbearing potential. For the purposes of this study, women of childbearing potential are defined as: All female subjects after puberty unless they have age-related natural (spontaneous) amenorrhea  $\geq 12$  consecutive months and increased follicle-stimulating hormone (FSH)  $> 40$  mIU/mL, are surgically sterile, or are sexually inactive.
11. Highly effective contraception (ie, methods with a failure rate of less than 1% per year) for both men and women if the risk of conception exists. See Section 12, Appendix III for further guidance on methods of contraception that are considered highly effective.

**Note:** The effects of avelumab on the developing human fetus are unknown; thus, women of childbearing potential and men must agree to use effective contraception, as defined in Section 12, Appendix III, or as stipulated in national or local guidelines. Highly effective contraception must be used from Clinical Screening, for the duration of the study treatment, and until at least 60 days after stopping avelumab. Should a woman become pregnant or suspect she is pregnant while she or her partner is participating in this study, the treating physician should be informed immediately.

### 5.3.2 Exclusion Criteria

1. Prior therapy with any antibody/drug targeting T cell coregulatory proteins (immune checkpoints) such as PD-1, PD-L1, cytotoxic T-lymphocyte antigen-4 (CTLA-4), 4-1BB, LAG-3, TIM-3 or anti-CD127. Prior therapy with a cancer vaccine is acceptable.
2. Concurrent anticancer treatment(s) (eg, cytoreductive therapy, radiotherapy [with the exception of \*palliative bone-directed radiotherapy and radiotherapy administered to superficial lesions], immune therapy, or cytokine therapy except for erythropoietin). Radiation to more than 30% of the bone marrow or with a wide field of radiation should not be used within 28 days prior to the first administration of avelumab and is prohibited throughout the study.

---

\*Palliative bone-directed radiotherapy should be within a limited field of radiation and for palliation only. It should be a short course, according to local institutional recommendation, and should be completed at least 7 days prior to the first administration of avelumab.

3. Major surgery for any reason, except diagnostic biopsy, within 28 days of the first administration of avelumab and/or if the subject has not fully recovered from the surgery within 28 days of the first administration of avelumab.
4. Concurrent use of nonpermitted drug(s) (see Section 6.5.2).
5. Rapidly progressive disease (eg, tumor lysis syndrome).
6. All subjects with active brain metastases, except those meeting the following criteria:
  - Brain metastases that have been treated locally, and have not been progressing for at least 2 weeks after the completion of therapy, and no steroid maintenance therapy is required, AND
  - No ongoing neurological symptoms that are related to brain localization of the disease (sequelae that are a consequence of the treatment of brain metastases are acceptable).

**Note:** Subjects with mild residual neurologic deficit that is permanent as a result of prior brain metastases after local treatment are eligible provided the residual lesion is stable for at least 4 weeks and without evidence of enlarging, and the subject is not on steroid therapy.

7. Previous malignant disease other than the target malignancies to be investigated in this study, with the exception of in situ carcinoma of the cervix, or adequately treated non-melanomatous cancers of the skin, or other malignancy treated at least 5 years previously with surgery and/or radiotherapy, and there is no evidence of recurrence since that time.
8. Subjects who have received any investigational product within a period of time that is less than the cycle length used for that treatment or equal to 28 days (whichever is shorter) prior to the first administration of avelumab.
9. Prior solid organ or bone marrow transplant.
10. Significant acute or chronic infections including, for example:
  - Uncontrolled acute infection.
  - Known history of testing positive for human immunodeficiency virus (HIV) or known acquired immunodeficiency syndrome. Subjects who do not know their HIV status are required to undergo HIV testing, subject to the provision of informed consent. Subjects who do not know their HIV status who are unwilling to undergo HIV testing are not eligible for the study (see Section 7.1.1).
  - Positive test for hepatitis B virus surface antigen and/or confirmatory hepatitis C virus ribonucleic acid (if antihepatitis C virus antibody tested positive); tests to be performed at Clinical Screening.
11. Active autoimmune disease that might deteriorate when receiving an immunostimulatory agent:

- Subjects with Type I diabetes, vitiligo, psoriasis, hypo- or hyperthyroid disease not requiring immunosuppressive treatment are eligible.
  - Subjects receiving immunosuppressive agents (such as steroids) for any reason should be tapered off these drugs before initiation of avelumab (with the exception of subjects with adrenal insufficiency, who may continue corticosteroids at physiologic replacement doses, equivalent to  $\leq 10$  mg prednisone daily). Subjects who are not allowed to taper off immunosuppressive agents should be excluded. Administration of steroids for other conditions through a route known to result in a minimal systemic exposure (topical, intranasal, intra-ocular, or inhalation) are acceptable.
12. Previous or ongoing administration of systemic steroids for the management of an acute allergic phenomenon is acceptable as long as it is anticipated that the administration of steroids will be completed in 14 days, or that the daily dose after 14 days will be  $\leq 10$  mg/day of prednisone or equivalent.
  13. Known severe hypersensitivity reactions to monoclonal antibodies (Grade  $\geq 3$  NCI-CTCAE v4.03), any history of anaphylaxis\*, or uncontrolled asthma (that is, 3 or more features of partially controlled asthma).
- \*Anaphylaxis is a severe, life-threatening, generalized or systemic hypersensitivity reaction. It is characterized by rapidly developing, life-threatening problems (CTCAE Grading 3-5).
14. Persisting toxicity related to prior therapy (including any prior investigational therapy) of Grade  $\geq 2$  NCI-CTCAE v4.03 (except  $<$  Grade 3 neuropathy and alopecia of any grade).
  15. Pregnancy or lactation.
  16. Known alcohol or drug abuse.
  17. History of uncontrolled intercurrent illness including but not limited to:
    - Hypertension uncontrolled by standard therapies (not stabilized to 150/90 mmHg or lower), or
    - Uncontrolled active infection, or
    - Uncontrolled diabetes (eg, hemoglobin A1c  $\geq 8\%$ ).
  18. Clinically significant (that is, active) cardiovascular disease: cerebral vascular accident/stroke ( $<$  6 months prior to enrolment), myocardial infarction ( $<$  6 months prior to enrolment), unstable angina pectoris, congestive heart failure (New York Heart Association Classification Class  $\geq$  II), or serious cardiac arrhythmia requiring medication (including corrected QT interval prolongation of  $>$  470 msec calculated according to Fridericia and/or pacemaker or prior diagnosis of congenital long QT syndrome).
  19. All other significant diseases (eg, inflammatory bowel disease, colitis, pneumonitis, and fibrosis), which, in the opinion of the Investigator, might impair the subject's tolerance of avelumab.
  20. Any psychiatric condition that would prohibit the understanding or rendering of informed consent or that would limit compliance with study requirements.

21. Vaccination within 28 days of the first administration of avelumab and throughout the study is prohibited, except for administration of inactivated vaccines (eg, inactivated influenza vaccines).
22. Legal incapacity or limited legal capacity.

